Because this is an open-label trial in which participants and their healthcare providers will know their randomized dose of aspirin, the CDRN will be asked to engage regularly with the healthcare providers in their network regarding the rationale for the trial and the importance of compliance with the randomized treatment assignment to minimize patient cross-over. These clinical engagement approaches will be designed to facilitate discussions with healthcare providers who will be asked not to change a participant's aspirin dose during the trial unless it is absolutely necessary to ensure participant safety. On the ADAPTABLE participant portal, participant will be reminded of the importance of adhering to the aspirin dose they were randomly assigned to unless their physician changes their dose for a major safety concern. Participant who cross over will be analyzed as they were originally randomized according to the intention-to-treat (ITT) principle.

III.C.5.b. Drug Discontinuation – Monitoring and Recommendations

Aspirin use will be collected via the responses to the participant questions during follow-up. During each follow-up contact, compliance with the randomized aspirin dose will be assessed. The occurrence of and reasons for discontinuing aspirin or changing the dose of aspirin will be ascertained. In the event of aspirin intolerance or bleeding, the decision to continue the randomized aspirin dose, convert to a lower or higher aspirin dose, or to discontinue aspirin therapy will be left to the treating physician's discretion. Participants who discontinue aspirin therapy altogether will remain in the trial for clinical outcomes follow-up according to the ITT principle.

If a female participant becomes pregnant or plans to attempt to become pregnant during study follow-up, then aspirin should be permanently discontinued. Furthermore, if a participant requires an oral anticoagulant during study follow-up, the treating physician should carefully consider whether to continue aspirin based upon the estimated bleeding risks of aspirin used together with an oral anticoagulant, based on the clinical context. Finally, participants who develop an intracranial hemorrhage or a life-threatening bleeding event during study follow-up should be considered for permanent discontinuation of aspirin, at the discretion of their treating physician.

III.C.5.c. Delinquent or Missing Follow-up

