Assuming an annualized event rate of 4.6% in the higher risk arm and a 15% RR reduction (annualized event rate 3.8% in the lower risk arm) leads to 88% power and requires 1322 primary outcome events.

For the primary safety endpoint of hospitalization for major bleeding, power calculations were based on

Table 6					
Overall annualized event rate (%)	Relative Risk	Annualized event rate in low risk group (%)	Annualized event rate in high risk group (%)	Number of Events	Power
4.2	0.800	3.7	4.7	1321	0.99
4.2	0.825	3.8	4.6	1320	0.96
4.2	0.850	3.9	4.5	1322	0.88
4.4	0.800	3.9	4.9	1381	0.99
4.4	0.825	4.0	4.8	1381	0.97
4.4	0.850	4.1	4.8	1383	0.89
4.6	0.800	4.1	5.1	1441	0.99
4.6	0.825	4.2	5.0	1442	0.97
4.6	0.850	4.2	5.0	1439	0.90
4.8	0.800	4.3	5.3	1501	1.00
4.8	0.825	4.3	5.3	1502	0.98
4.8	0.850	4.4	5.2	1503	0.92

estimated primary event rates of 2%, 2.5%, and 3% per year (in the higher dose arm); annualized rate of loss to follow-up of 5%; 2-sided significance level alpha of 0.05; 7,500 participants in each treatment arm; total enrollment of 38 months; and a maximum follow-up period of 50 months. The power of the chosen testing strategy to detect a statistically significant difference in hospitalization for bleeding under these assumptions is shown in **Table 7**. Under all event rate scenarios, there will be power greater than 85% to detect an RR reduction of 25%, and for event rates of 2.5% or greater, power will be close to 80% to detect an RR reduction of 20%.

III.F.6. Secondary Endpoints

Secondary endpoints include the components of the primary endpoint, coronary revascularization procedures, quality of life, and functional status (Section III.A.5.a). Time-to-event outcomes will be analyzed using the same approach as the one used for the primary endpoint. Variables collected on numerical scales will be analyzed as continuous variables. Linear repeated measures mixed model will be employed to compare the 2 treatments on the changes from baseline.

Table 7			
Annualized event rate in higher-dose arm	Relative risk reduction	No. of events	Power
2%	25%	436	86%
	20%	449	66%
	15%	461	42%
2.5%	25%	544	92%
	20%	559	76%
	15%	575	50%
3%	25%	651	96%
	20%	669	83%
	15%	688	58%

III.F.7. Prior Treatment Effect

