7.2 Populations for Analysis

The Intent-To-Treat (ITT) Population will consist of all patients randomized to a treatment group in the study regardless of their compliance with the study medication. For all ITT analyses, participants will be analyzed as randomized.

Patients who were inappropriately randomized due to administrative errors (excluding those taking prohibited medications) were withdrawn from the study prior to initiating study drug. These patients were included in the randomization scheme, but will have no study data beyond that and will not be included in the ITT population.

Given the pragmatic nature of the trial and the expected gaps in data on patient compliance with randomized dose, we will not define the per-protocol (PP) population. Sensitivity analyses are described in section 7.10 that address treatment compliance.

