7.3 Primary Effectiveness Comparison

The primary endpoint of this study will be event-free survival from the first event of a composite of all-cause death, hospitalization for nonfatal myocardial infarction, or hospitalization for nonfatal stroke. The primary effectiveness analysis will be performed in the ITT population based on randomized treatment assignment. Event-free survival rates will be compared using Cox proportional-hazards models, equivalent to the log-rank test, using censoring rules described in Section 7.5. The test will be two-tailed and will be performed at an overall α of 0.05. The proportional hazards assumption will be checked for the randomized treatment assignment using weighted Schoenfeld residuals. If there is evidence of non-proportionality, a cautious interpretation of the Cox model hazard ratio will be encouraged, and non-parametric event rate estimates will be emphasized (see below).

In addition to Cox regression, cumulative endpoint event rates will be estimated as a function of follow-up time in each treatment group using Kalbfleisch & Prentice's nonparametric estimator of the cumulative incidence function (CIF). The Kalbfleisch & Prentice CIF estimator is equivalent to the Kaplan-Meier estimator when applied to endpoints that are not subject to competing risks. Cumulative endpoint event rates and differences in cumulative endpoint event rates will be

estimated and presented with 95% confidence intervals. These non-parametric analyses are important for descriptive purposes and will be a focus of interpretation if the event rate curves cross. They may also be used to construct summary measures of treatment effect which are interpretable when the proportional hazards assumption is violated.

Sensitivity analyses for potential misclassification and under-reporting of endpoints and for nonadherence to randomized aspirin dose are described in Section 7.10. An additional sensitivity analysis will be performed to take clustering of patients within sites into account, using the robust sandwich covariance estimator.

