No formal adjustments for multiple testing will be performed. All main and sensitivity analysis results will be presented and left to the interpretation of the reader.

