7.10 Planned Sensitivity Analyses

Sensitivity analyses will be conducted to assess robustness of trial conclusions to 1) nonadherence to randomized aspirin dose and 2) under-reporting and misclassification of endpoint data. Sensitivity analyses will be focused on primary analysis of the primary efficacy and safety endpoints, but the methods may be generalized to key secondary endpoints. **Non-adherence**. A sensitivity analysis will be conducted in the ITT population in which participant-reported aspirin dose is added to the primary analysis Cox model as a time-varying covariate.

COVID-19. A sensitivity analysis will be conducted in the ITT population in which censoring for the primary efficacy endpoint will occur on December 31, 2019 the original study end date and prior to COVID entering the United States. Although we do not expect a differential impact of randomized aspirin dose, COVID-19 could drastically increase the observed primary efficacy endpoint.

Bayesian Analysis. As part of planned secondary analyses following the primary final report, a sensitivity analysis for the primary efficacy endpoint will be performed using a Bayesian proportional hazards model or a Bayesian piece-wise exponential non-proportional hazards model, pending assessment of the proportional hazards assumption. Using the Bayesian posterior distribution, we will calculate the posterior probability that the unknown treatment specific hazard ratio exceeds thresholds of 1.0, 1.05, 1.10, 1.15 and 1.20 and reciprocals of those numbers. Because Bayesian inferences may be sensitive to the choice of prior distribution, further sensitivity analyses will be performed and reported for a range of possible prior distributions.

Proportional hazards assumption holds.

Bayesian analysis requires the specification of a prior probability distribution representing prior information about the set of unknown model parameters before observing the study data. Because prior information about the treatment effect is limited, we will pre-specify a flat (uniform) prior for the Cox model regression coefficient. The selection of a uniform prior reflects the subjective assessment that prior information about the direction and magnitude of the treatment effect is neutral. It also allows posterior inferences to be dominated by the current study data as opposed to the prior.

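### The only adherence analysis adds reported dose to a Cox model that already contains arm, so its arm hazard ratio cannot show robustness to non-adherence

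*SAP*

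**What the plan says.** SAP 7.10 states the purpose: "Sensitivity analyses will be conducted to assess robustness of trial conclusions to 1) nonadherence to randomized aspirin dose". The whole method is one sentence, under which "participant-reported aspirin dose is added to the primary analysis Cox model as a time-varying covariate". SAP 7.2 makes this the only adherence analysis: citing "expected gaps in data on patient compliance with randomized dose, we will not define the per-protocol (PP) population", it sends treatment compliance to 7.10. Protocol III.F.2 defines a per-protocol population by a 50% compliance rule but attaches no analysis to it.

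The model being extended has arm as its only term. SAP 7.3 says "Event-free survival rates will be compared using Cox proportional-hazards models, equivalent to the log-rank test", and Protocol III.F.3 notes that this equivalence holds when there are no other covariates.

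The SAP text does not say which coefficient answers the question. The closing paragraph of SAP 7.7 says "All main and sensitivity analysis results will be presented and left to the interpretation of the reader".

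On why doses change, Protocol III.C.5.b says "In the event of aspirin intolerance or bleeding, the decision to continue the randomized aspirin dose, convert to a lower or higher aspirin dose" is a matter for the treating physician, as is stopping aspirin. It adds that "The occurrence of and reasons for discontinuing aspirin or changing the dose of aspirin will be ascertained".

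**The concern.** Reported dose is measured after randomization and is the route by which assignment is expected to act. With dose in the model, the arm coefficient keeps only what assignment does other than through dose. A reader who compares it with the ITT HR could see a true effect vanish and conclude that the result is fragile.

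The dose coefficient is an as-treated contrast. It is valid only if dose change is unrelated to prognosis given the covariates in the model, and the planned model has none. The protocol links dose change to intolerance and bleeding. That these predict death, MI or stroke is an assumption here.

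There are two smaller gaps. Dose coding is not given for participants who stop or take another dose. And 7.10 covers the bleeding endpoint, whose primary model in SAP 7.4 is Fine and Gray, so there is no primary Cox model for safety to extend.

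**Working it through.** The plan gives no figure for this analysis, so there is none to reproduce. HRs are 81 vs 325 mg. Switching is written as % of the 325 mg arm / % of the 81 mg arm.

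**Inputs.** The documents give no switching rate for this trial. The 35% is the 6-month switching figure from the non-randomized registry in Protocol II.A. The other rates and the prognostic strengths are assumptions. The main simulation used 2 million participants per scenario, with SEs scaled to 15,000 (about 1,265 to 1,394 events, mean follow-up 2.1 years). Switches fell uniformly over 6 months. A prognostic factor had SD 0.8 on the log hazard, and switching log-odds were 0, 0.3 or 0.5 per SD of it. Poisson regression on fine intervals approximated Cox. Simulation error on an HR is about 0.01 to 0.02.

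**Step 1: what the coefficients estimate.** Let A = 1 for assignment to 81 mg and D(t) = 1 while 81 mg is reported. The planned model is h(t) = h0(t)·exp(a·A + d·D(t)). If only dose taken matters, with θ = ln 0.85 = −0.1625, and switching is unrelated to risk, then a = 0 and d = θ. The arm HR is 1.00 whatever θ and whatever the switching rate. The ITT HR is roughly exp{θ·(p81 − p325)}, where p81 and p325 are the shares of each arm taking 81 mg after switching. This ignores time before the switch.

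| Switching | p81 − p325 | ITT, formula | ITT, simulated | Planned arm HR | Planned dose HR |
|---|---|---|---|---|---|
| 35/5 | 0.95 − 0.35 = 0.60 | 0.907 | 0.904 | 1.001 | 0.857 |
| 20/10 | 0.90 − 0.20 = 0.70 | 0.892 | 0.889 | 0.999 | 0.855 |
| 10/10 | 0.90 − 0.10 = 0.80 | 0.878 | 0.889 | 1.002 | 0.865 |
| 35/35 | 0.65 − 0.35 = 0.30 | 0.952 | 0.936 | 0.995 | 0.852 |

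A separately built start-stop Cox simulation used 15,000 participants, 38 months' accrual, 50 months' maximum follow-up and 5% annual loss (SAP 7.6). It gave arm HRs of 0.99 to 1.02 with 325-to-81 switching from 5% to 45%. The SE of the log arm HR was 0.071 to 0.135, against 0.053 to 0.054 for ITT. With complete adherence, arm and dose are collinear and the model cannot be fitted.

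**Step 2: no dose effect, prognostic switching (log-odds 0.3 / 0.5).** ITT stays at 0.99 to 1.01.

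| Switching | Planned arm HR | Planned dose HR |
|---|---|---|
| 35/5 | 0.911 / 0.873 | 1.157 / 1.251 |
| 20/10 | 0.949 / 0.918 | 1.071 / 1.106 |
| 10/10 | 1.017 / 1.005 | 0.98 to 1.00 |
| 35/35 | 1.004 / 0.996 | 0.98 to 1.00 |

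The two coefficients err in opposite directions and cancel in the ITT contrast: at 35/5, 0.873 × 1.251^0.60 ≈ 1.00. With stronger assumed confounding, the second simulation gave null arm HRs of 0.78 to 0.86, nominally significant in 42% to 97% of trials.

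**Step 3: true dose HR 0.85, prognostic switching.** The planned dose HR is 0.967 / 1.067 at 35/5, 0.906 / 0.932 at 20/10, and 0.83 to 0.85 when switching is symmetric.

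**Step 4: bleeding as the driver.** Protocol III.F.5 uses "estimated primary event rates of 2%, 2.5%, and 3% per year (in the higher dose arm"). Take 2.5% per year on 325 mg, 20% lower on 81 mg, and no direct dose effect. Assume 60% / 10% change dose after a bleed and the endpoint hazard doubles. The HR with no switching is 0.99. If bleeding is the only cause of change (3.1% / 0.4% of participants), the arm HR is 0.58 (SE 0.21) and the dose HR 1.74. With unrelated switching of 10/10, 20/10 or 35/5 added, the arm HR is 0.93, 0.96 or 0.98 and the dose HR 1.09, 1.05 or 1.03.

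**Step 5: dose coding.** With 35% switching, 10% stopping and no confounding, the second simulation gave an arm HR of 1.012 with dose as categories and 0.969 with dose in mg.

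**Step 6: alternatives.**
- Planned model plus the prognostic factor: dose HR 0.983 to 1.005 under no effect, 0.844 to 0.859 when the truth is 0.85.
- Arm-only model, censored at departure and weighted on the factor: 0.988 to 1.009 and 0.847 to 0.866.
- With only a proxy for the factor (correlation 0.7), no true effect: adjusted dose HR 1.08 to 1.12 at 35/5 and 1.04 to 1.05 at 20/10; weighted arm HR 1.03 to 1.06 and 1.01.
- With the factor unmeasured, the weighted arm HR is 1.06 to 1.11 at 35/5 and 1.02 at 20/10.

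**The case against.** The SAP never says that the arm HR will be read. If the dose HR is read, it is about right whenever switching is unrelated to risk or balanced between arms. The table shells named in SAP 8 are not available and might settle both coefficient and coding. The SAP 7.7 sentence about the reader follows one on multiple testing, so it says little about coefficients.

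The size is also open to challenge. The 35% comes from patients after acute MI and PCI, and the 5% is assumed. Protocol II.D.2 reports stopping or dose reduction between 2.7% and 19.2% in earlier aspirin trials, but not the asymmetry between doses that drives the null bias. The planned model is imprecise: its log-HR SE is about 0.085 at 20/10 and 0.08 at 35/5. The 20/10 null bias is therefore about 0.6 to 1.2 SE, and only the 35/5 dose bias (1.8 to 2.8 SE) clearly exceeds noise. The weighted fix relies on the same incomplete dose reports that led the SAP to drop a per-protocol population. SAP 2 frames the trial as a test of an aspirin policy, for which ITT is the right primary analysis.

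Most of this stands as a limit on size, and the Fine and Gray gap is largely drafting. None of it makes the arm HR a measure of robustness to non-adherence, which follows from the model's form and needs no particular switching rate. Nor does it supply the covariates that the dose HR needs.

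**Conclusion.** The concern holds. As written, the one adherence analysis yields an arm HR of about 1.0 when dose matters and switching is unrelated to risk. Its dose HR is unadjusted for the reasons people change dose. That the arm HR cannot do the stated job is certain; the size of any bias is not. With no dose effect, bias ranges from none under symmetric switching to a dose HR of 1.25 at 35/5 under the main assumptions. It is small when bleeding drives only a minority of changes. These sizes rest on assumed switching rates and assumed prognostic strength. The primary ITT result is unaffected. The damage would be to the only evidence the SAP offers on adherence in an open-label trial.

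**What to change.** In SAP 7.10, replace the sentence with an arm-only Cox model that censors at the first reported departure from assigned dose. If only sustained departures count, define them (for example, two consecutive scheduled reports) and censor at the second, so that no later information is used.

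- **Weights.** Use stabilized inverse-probability weights for staying on assigned dose and for continuing to report dose, in the form Protocol III.F.8 describes for dropout. With assumed reporting stops of 15% / 8% per year, dose weights alone gave null HRs of 1.019 to 1.038, and both sets gave 0.997 to 1.006.
- **Covariates.** Baseline characteristics, pre-randomization aspirin dose, assigned contact interval, latest reported P2Y12 inhibitor, NSAID and PPI use, and time-updated non-endpoint events. For efficacy these events are bleeding hospitalization and revascularization; for bleeding they are MI, stroke and revascularization.
- **Gaps.** State a rule, for example carry the last report to the next scheduled contact and then censor. Report how many participants have no dose report.
- **Departures.** Tabulate them by arm and collected reason.
- **Bleeding.** Name the model, for example cause-specific Cox.

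If the arm-plus-dose model is kept, add prognostic covariates, state the dose coding, name the dose coefficient as the result, label it descriptive, and do not read the arm coefficient as adherence robustness.

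The cost is SAP wording and programming, with no new data collection. The weighted analysis assumes no unmeasured confounding of dose change or of reporting. It loses some precision: log-HR SE 0.059 to 0.065 at 35/5 and 20/10, or 0.064 to 0.072 with reporting stops, against 0.054 to 0.056 for ITT. The lighter option is less precise than the weighted one except when switching is heavy in both arms (35/35: 0.055 to 0.060 against 0.067 to 0.072 weighted). Medication reports are annual after the first contact, so early changes rest on that first report, and participants without self-report add little or no dose information.

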7.5 Censoring Rules

In the event that a patient does not experience an efficacy or safety endpoint, the patient will be censored at the earliest of study end date or maximum follow-up time point at which the patient can be reasonably assumed to be event free. The maximum follow-up time point will be determined from any of the following data sources: CDM censor date, CMS censor date, private health insurance censor date, or the web portal censor date (last point of contact).We expect the study end date to occur on or before all follow-up time points; however, for completeness, censoring dates are defined below. Patients who withdraw consent for trial follow-up will be censored at the time consent is withdrawn. Patients who consent to limited participation follow-up will be censored at the earliest follow-up time point as delineated.

The censoring date for CDM data will be at the site-specific censoring date, which is determined by the PCORnet Distributed Research Network Operations Center based on data curation query results. The censoring date for CMS will be the minimum of the end of enrollment in fee-forservice or the last date claims data are available. The censoring date for private health insurance claims will be the minimum of the end of claims enrollment or the last date claims data are available.

Time to event modeling will include the first occurrence of an event where the time to event is calculated as the event date – randomization date +1.

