For the primary analysis (and related secondary analyses), we make the following assumptions:

- Death is reported without error.
- Other components of the primary endpoint may be subject to under-reporting and misclassification but these errors are non-differential, i.e. probability of an error is consistent across randomized treatment groups.
- Patient self-report with confirmation is assumed to have nearly perfect specificity since incorrect self-reports will be excluded by examination of medical record. There may be some under-reporting since identification of the event depends on self-report. Some selfreported events may not be confirmed or contradicted if participant did not consent to confirmation process.
- CDM endpoints may be under-reported since participants may be treated for events outside the CDM health systems or events within the health system may be missed. Misclassification may occur due to imperfect electronic phenotype definitions.
- Claims data (CMS and private) is assumed to be complete for enrolled participants and changes in enrollment status are independent of trial outcome. Misclassification may occur due to imperfect electronic phenotype definitions.

We will perform two sets of sensitivity analyses: 1) to assess impact of under-reporting on the primary analysis and 2) to assess impact of misclassification on the primary analysis. Because available data sources vary across participants, we summarize the potential for error due to under-reporting and misclassification according to each potential combination of available data. To simplify classification of participants, we will not attempt to account for changes in data sources over time, but rather classify participants according to data sources available for more than half of follow-up time.

	Data sources available			Potential error		
Scenario	Self- report	Out of Network Confirmation	CDM	Claims (CMS or private)	Under- reporting	Misclassification
1	Х				Yes	Yes
2	Х	Х			Yes	No
3	х		Х		Yes	Yes
4	Х			Х	No	Yes
5	Х		Х	Х	No	Yes
6			Х		Yes	Yes
7				Х	No	Yes

8		Х	Х	No	Yes
9*				Yes	No

*Only information is vital status check at end of trial.

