To assess impact of under-reporting due to participants moving or seeking care outside of the CDM health system, we will repeat the primary analysis modifying the censoring rules for CDM data such that the censoring date will be the last date the patient encountered the health system. This will include inpatient and outpatient visits, labs, vitals and prescription medication fills. All other censoring dates will remain the same.

Under the assumption that under-reporting is non-differential between treatment groups, the impact on primary analysis inference would be a loss of power. If the primary result is non-significant then we will assess overall impact of under-reporting, by performing a tipping point analysis to identify how many events would have to be missed to achieve significance. We will take an approach that is adapted and simplified from that described by Little et al (2016) for a sensitivity analysis for missing data. A Weibull model of the primary endpoint will be fit to the entire ITT population, with independent variables including an indicator that participant is at risk for under-reporting (Scenarios 1, 2, 3 and 6 in the table) and selected baseline characteristics. Other independent variables may be considered. Events will be sequentially added for those participants at risk of under-reporting across treatment groups. For each increment, *i* events will be imputed from the Weibull model 1000 times. A Cox model as specified for the primary analysis will be fit to the resulting dataset and treatment effect hazard ratio will be estimated, with standard errors adjusted using standard multiple imputation combining rules. The increment will be increased until the upper limit of the 95% CI for the HR of the treatment effect crosses 1.0.

To assess impact of misclassification of electronic phenotype definitions, we will repeat the primary analysis modifying the code-based definitions of primary endpoints to include codes in 1) principal position only and 2) any position.

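### The under-reporting sensitivity analysis (SAP 7.10) shortens follow-up only for event-free patients, so where the CDM date decides censoring it raises event rates even if no event was missed

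*SAP*

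**What the plan says.** In the primary analysis the CDM date belongs to the site and does not depend on the patient's own visits: "The censoring date for CDM data will be at the site-specific censoring date" (SAP 7.5).

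SAP 7.10 changes this to address patients who move away or seek care elsewhere. For CDM data, "the censoring date will be the last date the patient encountered the health system". On what counts as an encounter: "This will include inpatient and outpatient visits, labs, vitals and prescription medication fills". For the remaining sources: "All other censoring dates will remain the same".

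Three further statements decide what the change does:

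- **Who is censored.** SAP 7.5 sets a censoring date when a patient "does not experience an efficacy or safety endpoint, the patient will be censored at the earliest of study end date" or the maximum follow-up time point. A patient with an event keeps the event date.
- **How sources combine.** "The maximum follow-up time point will be determined from any of the following data sources: CDM censor date, CMS censor date", private insurance and the portal. Limited-participation patients are the exception: "Patients who consent to limited participation follow-up will be censored at the earliest follow-up time point as delineated".
- **Deaths.** SAP 7.10 assumes "Death is reported without error", so a death counts however long after the last encounter it occurs.

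Neither document removes an event that falls after the last encounter, and neither comments on the resulting asymmetry.

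**The concern.** A hospitalization for MI or stroke captured in the CDM is itself an inpatient encounter. A patient with such an event is therefore observed up to the event by construction, and deaths are kept too. An event-free patient is cut back to the last visit, lab, vital sign or fill, even when the next visit was simply not yet due. How much follow-up a patient contributes then depends on the outcome.

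The analysis exists to show whether care outside the network distorts the result. If its event rates exceed those of the primary analysis, a reader cannot tell under-reporting from this artefact. SAP 7.7 leaves main and sensitivity results to the reader's interpretation, so the artefact would be published without a warning. The amount of time removed also depends on how often patients are seen. A difference in encounter frequency between the open-label arms would therefore carry into the hazard ratio.

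**Working it through.** The plan states no figure for this analysis, so there is none to reproduce.

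**Inputs from the documents.** Enrollment lasts 38 months and maximum follow-up is 50 months (SAP 7.6), so administrative follow-up C runs from 12 to 50 months, taken as uniform on 1 to 4.167 years (width 3.167). The overall event rate is 4.2% per year (Protocol III.F.5, Table 6).

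**Assumptions not in the documents.** No event is missed. Encounters are Poisson, with rates varying between patients as a gamma distribution of shape 2 and mean m per year. The CDM date decides censoring for a share s of patients.

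**Time removed per event-free patient.** At encounter rate v the mean time from last encounter to C is (1 − e^(−vC))/v. Averaged over the gamma distribution with θ = m/2, this is C/(1 + θC). Averaged over C:

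D = (1/θ) × [1 − ln((1 + 4.167θ)/(1 + θ))/(3.167θ)]

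- m = 2: D = 1 − ln(5.167/2)/3.167 = 0.700 years
- m = 4: D = 0.5 × [1 − ln(9.333/3)/6.333] = 0.410 years
- m = 12: D = (1/6) × [1 − ln(26/7)/19] = 0.155 years

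**Rate inflation.** The event-free proportion is S = (e^(−0.042) − e^(−0.175))/(0.042 × 3.167) = 0.898. Person-years per patient are P = (1 − S)/0.042 = 2.432 (S unrounded). Inflation = P/(P − s·S·D) − 1. For m = 2 and s = 1 this is 2.432/(2.432 − 0.629) − 1 = 34.9%.

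| Encounters/yr | s = 10% | 25% | 50% | 100% |
|---|---|---|---|---|
| 2 | 2.7% | 6.9% | 14.8% | 34.9% |
| 4 | 1.5% | 3.9% | 8.2% | 17.9% |
| 12 | 0.6% | 1.5% | 2.9% | 6.1% |

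The formula applies the average D to event-free patients, whose C is slightly shorter. Simulation without that shortcut gives 34.6% and 17.8% at s = 100%, and 6.9% and 3.9% at 25%, for 2 and 4 encounters per year. If all patients have the same encounter rate, the inflation is smaller: 22% and 10% at s = 100%, 4.7% and 2.4% at 25% (simulated at 4.5% per year).

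**Hazard ratio, equal encounters.** D is the same in both arms and cancels. In simulation a true 1.00 stays at 1.00 and 0.850 becomes 0.850-0.853.

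**Hazard ratio, 10% more encounters in one arm, true value 1.** The ratio of rates is (P − s·S·D₀)/(P − s·S·D₁), with D₁ at 1.1m: 0.654 for m = 2.2 and 0.379 for m = 4.4.

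- 2 per year: 0.998 at s = 10%; (2.432 − 0.314)/(2.432 − 0.294) = 0.990 at 50%; 0.977 at 100%
- 4 per year: 0.999 at 10%; 0.994 at 50%; 0.987 at 100%

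Cox fits to simulated data at s = 100% give about 0.975 and 0.985. With the planned 1322 events the standard error of the log hazard ratio is 2/√1322 = 0.055. A shift to 0.990 (log −0.010) is thus under 0.2 standard errors.

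**Is the asymmetry the cause?** A rule that stops counting both events and event-free time after a 12- or 18-month gap was simulated with a true rate of 4.5% per year, constant encounter rates and s = 100%. The rate stayed at 4.49-4.53% per year, against 4.91-5.49% under the SAP rule. The hazard ratio stayed within about 0.3% of the primary one with encounters of 2.4 vs 2, 4.8 vs 4 or 3 vs 2 per year. The SAP rule gave about 0.96, 0.98 and 0.92 in the same settings.

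**The case against.** The strongest reply is that the new date will rarely matter. Because the latest source date is used, a shortened CDM date has no effect where a portal contact or claims run later. Contacts are due every 3 or 6 months (Protocol III.C.5), there is an end-of-study assessment (III.C.4), and the call center and a locator service pursue final contact (III.E.4). SAP 7.5 itself expects study end to come no later than the source dates. Patients at high cardiovascular risk may also have many more than 2-4 encounters a year once labs and fills count.

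This stands as a limit on size. A reader might infer from the SAP 7.10 rule that every event-free patient is cut back. SAP 7.5 does not support that, and the 100% column is only an upper bound. But the share is not shown to be negligible. Claims cover only a portion of participants and lag in the final months (Protocol III.E.4), the portal date is only the last contact, and the scenario table in SAP 7.10 includes patients with CDM data alone. If the share is tiny, the analysis tests almost nothing.

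A reader might also infer that the rule creates a treatment difference. That needs unequal encounter frequency. The open-label design makes it possible, but the documents give no evidence of it. With equal frequency the hazard ratio does not move.

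**Conclusion.** The rule is wrong as written, in one supportive analysis. Where the CDM date decides censoring, it raises event rates without any missed event. For assumed shares of 10-50% the inflation is about 3-15% at 2 encounters a year, 1.5-8% at 4 and 0.6-3% at 12. The hazard ratio is essentially unaffected with equal encounter frequency. With an assumed 10% excess in one arm it moves to about 0.990-0.999 at those shares and 2-4 encounters a year. Share, encounter rates and arm difference are all assumptions.

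It would be too strong to conclude that the trial's main result is biased: the primary analysis uses the site-level date and is untouched. The point merits correction because the analysis cannot answer its own question as specified and the repair is cheap.

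**What to change.** In SAP 7.10, replace the last-encounter rule with one that does not depend on outcome:

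- CDM coverage ends when a prespecified interval has passed since the previous encounter without a new one, capped at the site-specific date. Twelve months is an example; run another length, such as 18 months, as a check.
- Once CDM coverage has ended and neither claims nor the portal covers the patient, count neither later events nor later event-free time.
- Keep the other censoring dates, and report encounters per patient-year by arm.

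Simply adding 12 months to the last encounter of event-free patients would not be enough. Events would still be treated differently, and about 7.9% inflation would remain at 2 encounters a year if the CDM date decided censoring for everyone.

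The cost is a short text change and a small program change. With a 12-month gap, about 1.5-14% of events drop out of this sensitivity analysis at shares of 10-50% and 2-4 encounters a year. For patients who really left the system, uncovered time up to the chosen interval is still counted.
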